#### PFIZER CONFIDENTIAL

Redacted

Page 36 of 55

by the sponsor. The SAP may modify the plans outlined in the protocol; any major modifications of primary endpoint definitions or their analyses would be reflected in a protocol amendment.

#### 9.8. Quality Control

Data from the eCRF will be stored in the study database. The database will be housed and managed by ARW during the study and analysis. Any data transfers to Pfizer will be carried out via a Secure File Transfer Protocol (SFTP) to ensure any international transfers are safeguarded. ARW's data server is based within the UK. Following completion of the study, the study database will be archived and subsequently permanently deleted, in accordance with ARW's and Pfizer's Master Services Agreement.

Version control will be used during the development of all data collection materials to ensure there is an auditable record of requested updates and changes are available.

The eCRF data will be captured within a password-protected, CFR Part 11 compliant EDC platform. In addition, each individual eCRF will be reviewed by 2 members of the project team to check for logical and medical consistency. Queries will be raised throughout the data management process and will only be closed following the satisfactory correction or explanation by each site. All queries will be logged within the EDC as part of the audit trail and will also be recorded within the data management plan (DMP). Following the review and sign-off of each eCRF by 2 members of the project team, the eCRF will be locked and will not be accessible for further data entry or changes. A database lock declaration form will be completed by the project manager and the form will be kept in the study file. The locked database will be saved into a folder with restricted access. A copy of the locked database will be made available to the analyst.

#### 9.9. Limitations of the Research Methods

- If subgroup numbers are low, comparisons will be limited. However, as this is purely a descriptive study with no statistical comparisons, the assessment of treatment patterns and effectiveness outcomes will not be affected by small sample sizes.
- InO treatment regimens and dosing schedules may differ per market, adding to the complexity of the assessment of effectiveness outcomes. Subgroup analyses could be conducted for subsets of patients receiving the same or similar treatment regimens and or dosage schedules.
- As patient data originates from multiple countries, sites and settings there may be some variability in the study results.
- The minimum follow-up period has been set to 3 months. Consequently, for a large number of patients, OS and event free survival (EFS) maybe not assessable. These patients will be censored for such analyses.

PFIZER CONFIDENTIAL

Redacted

- For the chart review, selection bias may arise. Site participation is influenced by willingness to take part, and may be based on workload, levels of consulting patients during the data collection period, or familiarity with the research nature of the study. Efforts will be made to seek waivers for informed consent to prevent the requirement for consent from being a biasing factor, eg, patients who are particularly severe may be unwilling/unable to consent which may bias the living sample of patients towards those with a more positive prognosis. Efforts will therefore be made to receive a waiver for consent to mitigate this potential bias.
- Missing data from the eCRF is a potential limitation to consider in this study. Some variables that we intend to collect may not be present within a patient's medical record and so cannot be extracted into the eCRF. To address this limitation, the standardised eCRF will undergo a thorough review process prior to implementation which will help ensure that the content is appropriate for the listed research objectives and can reasonably be expected to be captured within patients' medical notes. Further, the eCRF will be designed in such a way that incomplete variables will be flagged and eCRFs will not be able to be locked until all variables have been completed. Despite these mitigations, it is expected that there will be an embargo on data from CAR-T infusion onwards for a proportion of patients (up to approximately 50%) in Spain due to an ongoing clinical trial, which will prevent data on CAR-T treatment patterns or post-CAR-T outcomes from being assessed. Nonetheless, given the paucity of data for patients receiving InO as bridging therapy to CAR-T, these patients will be included given this limitation will not impact the primary objective of the study.

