### 8. RESEARCH QUESTION AND OBJECTIVES

What are the demographics, clinical characteristics, treatment patterns and outcomes of R/R ALL patients treated with InO as a bridging therapy to CD19-directed CAR-T therapy in the RWD? This research question will be addressed through the following research objectives:

- (Primary objective) To describe the demographics and clinical characteristics of R/R ALL patients treated with InO as a bridging therapy for CAR-T
- (Secondary objective) To describe relevant treatment effectiveness outcomes for the study population, including response to treatment, time-to-next salvage treatment and survival
- (Secondary objective) To describe InO treatment patterns in the study population, including the use of InO in combination or monotherapy, timing of treatment and dosage information

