#### 9.5. Study Size

This study is purely descriptive and there will be no limit on the sample size in terms of patients meeting the eligibility criteria. The estimated number of patients based on the feasibility study is expected to be n = 79.

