#### 9.7. Data Analysis

The study is not intended to test hypotheses and is primarily descriptive in nature, therefore descriptive analysis will be conducted to meet the majority of the pre-specified objectives. Frequencies and percentages will be reported for categorical variables, including the percentage of missing/unknown data, while counts, number of missing, means, medians, standard deviations (SDs), first and third quartiles, minimum and maximum values will be reported for continuous numeric variables. Where applicable, all estimates will be described with accompanying 95% confidence intervals (CI). Outcomes such as OS will be assessed via time to event analyses, with KM curves and 95% CI estimated for KM curves outputted. This will be calculated using variables in the CRF. For example, OS will be calculated from the first dose of InO to point of death. Censoring will be applied if the patient is alive at the point of data capture.

Data analysis will be aligned with data extracted/collected from all data sets. Where specific variables or outcomes cannot be assessed/described subgroup analyses could be conducted for a subset of patients from certain data sources.

All analyses will be conducted using Stata 17 software, version 17 or the latest available version (StataCorp, College Station, Texas).

Detailed methodology for summary and statistical analyses of data collected in this study will be documented in a statistical analysis plan (SAP), which will be dated, filed, and maintained

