#### Comments:

Exposure, outcomes, covariates, and other characteristics are described in **Section 9.3** of the protocol. This section captures the variables which will be captured/defined through the data provided by the sites submitted via the CRF and secondary data sources. The protocol itself does not indicate the exact variables which will be provided by the data sources themselves. These will be described in detail within the study SAP.

The coding system for any exposures, outcomes or covariates is not applicable to the secondary data source or the sites where a chart review will be used for data collection. There is no linkage that will be utilised.

Section	on 10: Analysis plan	Yes	No	N/A	Section Number
10.1	Are the statistical methods and the reason for their choice described?	$\boxtimes$			9.7
10.2	Is study size and/or statistical precision estimated?	$\boxtimes$			9.5
10.3	Are descriptive analyses included?	$\boxtimes$			9.7
10.4	Are stratified analyses included?		$\boxtimes$		
10.5	Does the plan describe methods for analytic control of confounding?		$\boxtimes$		
10.6	Does the plan describe methods for analytic control of outcome misclassification?		$\boxtimes$		
10.7	Does the plan describe methods for handling missing data?				9.3, 9.7 and 9.9
10.8	Are relevant sensitivity analyses described?		$\boxtimes$		
Comm					

Comments:

Section	on 11: Data management and quality control	Yes	No	N/A	Section Number
11.1	Does the protocol provide information on data storage? (eg, software and IT environment, database maintenance and anti-fraud protection, archiving)	$\boxtimes$			9.8
11.2	Are methods of quality assurance described?	$\boxtimes$			9.6 and 9.8
11.3	Is there a system in place for independent review of study results?		$\boxtimes$		

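### Section 9.9 says small samples will not affect the effectiveness results because the study is descriptive; that is wrong, since its planned 95% intervals widen as numbers fall

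*Protocol*

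**What the plan says.** The first limitation in Section 9.9 begins by accepting that comparisons will be limited if subgroups are small. It then gives the study's descriptive nature, and the absence of any comparison, as the reason why "the assessment of treatment patterns and effectiveness outcomes will not be affected by small sample sizes".

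The effectiveness outcomes are set by the secondary objective in Section 8, "including response to treatment, time-to-next salvage treatment and survival".

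Section 9.7 attaches 95% confidence intervals to estimates where applicable and adds: "Outcomes such as OS will be assessed via time to event analyses, with KM curves and 95% CI estimated for KM curves outputted".

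Section 9.5 gives the size: "The estimated number of patients based on the feasibility study is expected to be n = 79". It gives no expected interval width.

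Three other places bear on how many patients stand behind a given estimate:
- Inclusion criterion 3 (Section 9.2.1) admits patients who never received CAR-T.
- Section 9.9 expects data from infusion onwards to be embargoed for up to about half of the patients in Spain.
- Section 9.9 also allows for smaller groups: "Subgroup analyses could be conducted for subsets of patients receiving the same or similar treatment regimens and or dosage schedules".

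In Section 7 the protocol discusses a retrospective chart review of fourteen patients given InO before CAR-T, and tells the reader to treat its outcomes very cautiously because it was so small.

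**The concern.** The sentence draws the wrong conclusion from a correct premise. A study with no hypothesis test has no power to lose. It still produces estimates, and the sampling error of an estimate depends on how many patients or events it rests on. The protocol plans to report exactly that error as 95% intervals, so the sentence contradicts its own analysis section. It also exempts this study from the caution that Section 7 applies to a similar but smaller one.

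A limitations section tells readers how far the results can be trusted. This study is designated a PASS, hopes to help confirm the safety of the approach (Sections 4 and 7), and is meant for publication (Section 12). Carried into the report, the sentence would encourage readers to take response and survival figures as firmer than they are, most of all for post-infusion outcomes and for regimen or dose subsets.

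**Working it through.** **Inputs**
- Expected n = 79 (Section 9.5). This is a feasibility count with no assumed rate, target width or formula behind it, so there is no precision figure of the plan's own to reproduce.
- 95% confidence level (Section 9.7), taken as two-sided.
- Embargo on data from infusion onwards for up to about 50% of Spanish patients (Section 9.9).
- Spain's share of the 79 is not stated: assumed 25% to 50%.
- Infusion rate is not stated: no value is put in.
- Regimen or dose subset sizes and event counts are not stated: illustrative values only.

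**1. A proportion in the full sample.** Half-width = 1.96 × √(p(1 − p)/n). With p = 0.5 and n = 79: 1.96 × √(0.25/79) = 0.110, or 11.0 points. Exact (Clopper-Pearson) intervals: 40/79 gives 39.1% to 62.1%; 55/79 (about 70%) gives 58.2% to 79.5%.

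**2. An outcome seen in nobody.** The two-sided 95% upper limit is 1 − 0.025^(1/n). With n = 79 this is 4.6%.

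**3. Outcomes that need post-infusion data** (response to CAR-T, later treatment), with the embargo alone at its stated upper bound of one half:
- Spain 25%: 79 × 0.25 × 0.5 ≈ 10 lost, 69 left; 1.96 × √(0.25/69) = 11.8 points.
- Spain 50%: 79 × 0.50 × 0.5 ≈ 20 lost, 59 left; 1.96 × √(0.25/59) = 12.8 points.

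This treats every embargoed patient as one who would otherwise have supplied such data. Patients never infused would reduce the numbers further, by an amount the protocol does not let us calculate.

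**4. Smaller subsets (sizes illustrative), proportion of 50%**

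| n | Half-width (points) | Exact 95% interval |
|---|---|---|
| 40 | 15.5 | 33.8% to 66.2% |
| 20 | 21.9 | 27.2% to 72.8% |
| 10 | 31.0 | 18.7% to 81.3% |

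**5. Time-to-event outcomes.** Here the number of events governs precision. Under an exponential approximation, the 95% interval for a median is the estimate multiplied by exp(±1.96/√d), where d is the number of events. For d = 60 the factors are 0.78 to 1.29; for d = 20, 0.65 to 1.55; for d = 10, 0.54 to 1.86. Section 9.9 itself says that overall and event-free survival may not be assessable for many patients, who will be censored, and that lowers d.

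Every planned interval therefore depends on n or on the number of events, which is what the sentence denies.

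**The case against.** The kindest reading is that the sentence, coming straight after a remark on subgroup comparisons, means only that no power is lost. That does not rescue it. Comparisons were dealt with in the sentence before, and this one goes on to say that the assessment of effectiveness outcomes is itself unaffected.

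It can also be said that the printed intervals will show the imprecision anyway, that the same section warns about survival follow-up and the embargo, and that no figure or analysis in the protocol is wrong. All of that stands. It limits the point to a misstatement in the limitations section. It does not make the statement true.

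Several stronger readings are tempting, but the documents do not support them:
- **That 79 is too few or needs a power calculation.** A descriptive review of all eligible patients needs neither.
- **That overall survival, response to InO and veno-occlusive disease rest on about 50 patients.** Overall survival runs from the first InO dose (Section 9.7), so all included patients enter and an embargo would only shorten follow-up. Response to InO is recorded after the first and last InO cycles, and veno-occlusive disease at any time (Section 9.3); neither requires infusion. Veno-occlusive disease is also listed under the primary objective, so the disputed sentence does not clearly cover it.
- **That country subgroups of a particular size are planned.** Section 9.9 names only regimen or dose subsets, and only as a possibility. The ENCePP checklist in Annex 2 answers No on stratified analyses.
- **That the checklist is wrong on precision.** The item reads "Is study size and/or statistical precision estimated". Section 9.5 does give a size, so a Yes is defensible.
- **That the protocol should set a minimum subset size for reporting percentages.** This is a matter of preference that can sit in the statistical analysis plan.

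**Conclusion.** The point holds as a misstatement in Section 9.9 that should be corrected. At n = 79 the 95% half-width for a proportion near 50% is about 11 points, and zero observed events leaves a two-sided upper limit of 4.6%. These two results need only the protocol's own size and confidence level.

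For outcomes that depend on infusion and later data, the half-width is about 12 to 13 points with 69 to 59 patients. That range rests on an assumed Spanish share of 25% to 50%, the embargo at its upper bound, and no loss from patients never infused. The figures for smaller subsets and for medians are illustrations of scale, not predictions. The conclusion rests on none of these assumptions. No planned analysis is affected; what changes is how much confidence the protocol tells readers to place in its estimates.

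**What to change.** In Section 9.9, replace the sentence. Say that the descriptive design means no hypothesis is tested, but that small numbers widen the confidence intervals and limit interpretation, especially for post-infusion outcomes and for any regimen or dose subset.

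In Section 9.5, add the expected 95% half-width at n = 79 (about 11 points at 50%) and for an assumed range of patients with post-infusion data. The assumptions on Spain's share, the embargo and the infusion rate should be stated. The sponsor may be able to replace the 59 to 69 used here with figures from the feasibility study.

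The cost is a few lines of text in two sections. No patients, data items or analyses are added. The protocol's account of its own reliability becomes less favourable, and correct.

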### Patient demographics:

Variable	Role	Data source(s)	Operational definition	Time-point
Patient's biological sex	Primary objective	eCRF	Patient's biological sex	N/A
Patient's race/ethnicity	Primary objective	eCRF	Patient's race/ethnicity	N/A
Patient Hispanic/Latin/Spanis h origin	Primary objective	eCRF	Origin	N/A
Patient's BMI	Primary objective	eCRF	Patient's BMI at index	1 st dose of InO (index)
Date of patient's death (if applicable)	Primary objective	eCRF	Time since death	Anytime up to/including data collection
Primary cause of patient's death (if applicable)	Primary objective	eCRF	Primary cause of death	Anytime up to/including data collection
Is the patient actively being monitored or have they been lost to follow up?	Primary objective	eCRF	Patient lost to follow up	Anytime up to/including data collection
Last date of activity for this patient (if lost to follow up)	Primary objective	eCRF	Time since last date of activity/ time since lost to follow up	Anytime up to/including data collection

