### **Clinical characteristics:**

Variable	Role	Data source(s)	Operational definition	Time-point
How many times has the patient received salvage therapy?	Primary objective	eCRF	Total number of salvage therapies received	Anytime up to/including data collection
On what date the patient received salvage therapy	Primary objective	eCRF	Date of each salvage therapy	Anytime up to/including data collection
Was the patient relapsed or refractory on receipt of this salvage therapy	Primary objective	eCRF	Relapse or refractory specification for each salvage therapy	Anytime up to/including data collection

Variable	Role	Data source(s)	Operational definition	Time-point
Duration of first remission following their ALL diagnosis before they relapsed? ( $\geq$ 12 months or <12 months)	Primary objective	eCRF	First remission duration	Since ALL diagnosis before relapse
Risk group of ALL based on cytogenic findings including: Philadelphia chromosome status, and cytogenetic, molecular and EMR positive	Primary objective	eCRF	Risk group of ALL at initial diagnosis	Initial ALL diagnosis, 1 st dose of InO (index)
ALL genetic alterations	Primary objective	eCRF	ALL genetic alterations at initial diagnosis	Initial ALL diagnosis, 1 st dose of InO (index
Laboratory test results	Primary objective	eCRF	Laboratory tests conducted at index	1 st dose of InO (index), After the last dose of InO prior to planned CAR- T infusion
Concomitant conditions	Primary objective	eCRF	Concomitant conditions present at index	1 st dose of InO (index)
ECOG performance status	Primary objective	eCRF	ECOG performance status at index	1 st dose of InO (index)
Patient diagnosed with veno-occlusive disease (VOD)	Primary objective	eCRF	Presence of VOD at any time	Anytime up to/including data collection
How was the patient diagnosed with VOD?	Primary objective	eCRF	VOD diagnosis	Anytime up to/including data collection
Did the patient receive defibrotide to manage their VOD?	Primary objective	eCRF	Defibrotide received	Anytime up to/including data collection
Most severe grade of VOD patient diagnosed with	Primary objective	eCRF	VOD grade at index	Anytime up to/including data collection
Bilirubin measured at most severe VOD diagnosis	Primary objective	eCRF	Measurement of bilirubin at most severe VOD diagnosis	Anytime up to/including data collection

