Bilirubin level at most severe VOD diagnosis	Primary objective	eCRF	Level of bilirubin at VOD diagnosis	Anytime up to/including data collection
Platelet count measured at most severe VOD diagnosis	Primary objective	eCRF	Platelet count at VOD diagnosis	Anytime up to/including data collection
Platelet count at most severe VOD diagnosis	Primary objective	eCRF	Platelet count result at VOD diagnosis	Anytime up to/including data collection

Variable	Role	Data source(s)	Operational definition	Time-point
Diagnosis of neutropenic sepsis	Primary objective	eCRF	Diagnosis of neutropenic sepsis	Anytime up to/including data collection
Risk factors for VOD	Primary objective	eCRF	Presence of risk factors for VOD at index	1 st dose of InO (index), Last dose of InO, At CAR-T apheresis, At CAR-T infusion
EMD	Primary objective	eCRF	Presence of EMD at R/R ALL diagnosis	At R/R ALL diagnosis
Is the patient's EMD bulky (Definition: presence of a nodal mass with a maximal dimension of >10 cm, or mediastinal mass >1/3 maximum transverse diameter of the chest)	Primary objective	eCRF	Bulky EMD at R/R ALL diagnosis	At R/R ALL diagnosis
Sites of extra-medullary disease	Primary objective	eCRF	Location of EMD at R/R ALL diagnosis	At R/R ALL diagnosis
CNS disease	Primary objective	eCRF	Presence of CNS disease at R/R ALL diagnosis	At R/R ALL diagnosis
CNS disease status	Primary objective	eCRF	CNS disease status at R/R ALL diagnosis	At R/R ALL diagnosis

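### Section 9.9 says the Spanish CAR-T trial embargo leaves the primary objective untouched, but Section 9.3 assigns to that objective VOD, neutropenic sepsis and death items whose windows run past infusion.

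*Protocol*

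**What the plan says.** Section 9.9 expects "an embargo on data from CAR-T infusion onwards for a proportion of patients (up to approximately 50%) in Spain due to an ongoing clinical trial". It accepts that CAR-T treatment patterns and later outcomes cannot be assessed for these patients, and retains them because "these patients will be included given this limitation will not impact the primary objective of the study".

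Section 8 words the primary objective briefly, as describing demographics and clinical characteristics. Section 9.3 then says item by item what belongs to it, through a role column and a time-point column. The row for VOD reads "Patient diagnosed with veno-occlusive disease (VOD) Primary objective eCRF Presence of VOD at any time Anytime up to/including data collection". The same role and the same open window are given to:

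- how VOD was diagnosed, defibrotide use, worst grade, and bilirubin and platelets at the worst episode;
- neutropenic sepsis;
- date and primary cause of death, follow-up status and last activity date;
- number, dates and relapsed/refractory status of salvage therapies.

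VOD risk factors are also primary, and one of their four assessment points is CAR-T infusion.

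Section 9.1 points the other way. It places the evaluation of baseline demographics and clinical characteristics at index, and leaves follow-up to treatment patterns and effectiveness outcomes.

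**The concern.** The statement in Section 9.9 is the stated reason for keeping the embargoed patients with no special handling of the primary items. It holds for items settled by index, such as sex, BMI, ECOG at index, or extramedullary and CNS disease at relapsed/refractory diagnosis. It does not hold for an item defined as "Presence of VOD at any time" when everything after infusion is withheld.

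The study is designated a PASS, and its rationale (Section 7) mentions possibly confirming the safety of the approach. VOD and neutropenic sepsis are the named safety items among the primary variables. If an embargoed patient with no event before infusion is entered as having none, that patient counts in the denominator for a period nobody could observe, and the proportion is biased downwards, towards looking safer.

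The general missing-data provision does not clearly catch this. Section 9.7 reports the percentage missing or unknown, but an answer of no, correct up to infusion, is not missing. Section 9.9 also says an eCRF cannot be locked until every variable is completed, and the protocol names no response for data that exist but are embargoed.

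**Working it through.** No stated power or precision figure is involved; n = 79 in Section 9.5 is a feasibility count. The check has two parts.

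**1. Windows against the embargo**

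| Item (role: primary objective) | Window in 9.3 | Observable if embargoed and infused |
|---|---|---|
| Sex, ethnicity, BMI, ECOG, concomitant conditions | none, or index | fully |
| EMD and CNS disease | relapsed/refractory diagnosis | fully |
| VOD presence, worst grade, management | to data collection | up to infusion only |
| Neutropenic sepsis | to data collection | up to infusion only |
| Date and cause of death | to data collection | unclear: 9.9 does not say whether vital status is embargoed |
| Salvage therapies | to data collection | up to infusion only |
| VOD risk factors | four points, the last at infusion | first three; the last is borderline |

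Salvage therapy is the weakest row, because lines after CAR-T are also captured separately under the secondary objectives. VOD and neutropenic sepsis are the clearest.

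**2. Scale**

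Inputs: N = 79 (Section 9.5); embargoed fraction of Spanish patients up to 0.50 (Section 9.9); Spain's share s is not stated, so a range is assumed.

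Embargoed patients m = 79 × s × 0.50:

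- s = 0.10: 79 × 0.10 × 0.50 = 4.0, about 4 patients (5%)
- s = 0.20: 79 × 0.20 × 0.50 = 7.9, about 8 patients (10%)
- s = 1/3: 79 × 0.333 × 0.50 = 13.2, about 13 patients (17%)
- s = 0.50: 79 × 0.50 × 0.50 = 19.8, about 20 patients (25%)

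These are upper counts for each share: 0.50 is the protocol's ceiling, and only patients who reach infusion lose data.

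To see what this does to one any-time proportion, suppose (an assumption, not a protocol figure) that VOD is recorded in 8 of 79 patients, none of them embargoed, and that every embargoed patient is entered as event-free. The recorded value is 8/79 = 10.1%. The highest value compatible with the data is (8 + m)/79:

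- m = 4: 12/79 = 15.2%
- m = 8: 16/79 = 20.3%
- m = 13: 21/79 = 26.6%
- m = 20: 28/79 = 35.4%

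These are worst-case bounds, reached only if every embargoed patient had the event after infusion. They show how much is left undetermined and are not estimates of bias.

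**The case against.** The strongest reply is that Section 9.9 is right and the table is loose. Section 9.1 ties baseline characteristics to index, which matches the short wording of the primary objective. The table also wavers: the operational definitions for worst VOD grade and for VOD risk factors refer to index, although their time-points extend beyond it. This stands in part. It means the no-impact statement is not simply false, and that relabelling the later items as secondary would be an acceptable remedy. It does not remove the conflict, because the role and time-point columns are explicit for VOD, neutropenic sepsis and death.

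A second reply is that Section 9.7 reports missing data, allows analyses in subsets where an outcome cannot be assessed, and leaves detail to a SAP that is not at hand. Nothing in the protocol says that embargoed data will be coded as no. That is correct, so the under-count is a risk and not a certainty. But the SAP would be written from a protocol telling it that the primary items need no special handling.

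A reader might also infer that overall survival will be inflated, since the censoring rule in Section 9.7 is "Censoring will be applied if the patient is alive at the point of data capture". The protocol does not support that. Section 9.7 does not mention embargoed patients or treat an unrecorded death as survival. Section 9.9 does not say whether vital status is embargoed. The screener asks whether the patient is alive, and the last activity date is collected for those lost to follow-up. Overall survival is also a secondary outcome, so it does not bear on the statement about the primary objective. Any figure for survival bias would need assumed infusion rates, assumed survival times and an assumed coding rule.

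**Conclusion.** The inconsistency is real and should be fixed. As written, Section 9.9 exempts the whole primary objective from the embargo, while Section 9.3 puts under that objective items whose post-infusion part may be unobservable for embargoed patients. If Spain supplies 10% to 50% of 79 patients and half of those are embargoed, about 4 to 20 patients (5% to 25% of the cohort) are affected, and only for the period after infusion. The direction of error for VOD and neutropenic sepsis is downwards if embargoed patients are entered as event-free; its size cannot be fixed from the protocol.

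This does not invalidate the study. It is descriptive and tests no hypothesis, the embargo is openly disclosed with its starting point and approximate extent, and including these patients is reasonable. For overall survival, the most that can be said is conditional: if vital status falls under the embargo, the censoring rule needs a date for these patients.

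**What to change.** Reconcile Sections 9.1, 9.3 and 9.9:

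1. In Section 9.9, limit the no-impact statement to primary items fixed before CAR-T infusion, and say that the any-time primary items are incomplete for embargoed patients.
2. For VOD, neutropenic sepsis, death and the other any-time items, either report (a) index to CAR-T infusion in all patients and (b) after infusion in non-embargoed infused patients, with each denominator stated; or give the post-infusion part a secondary role in Section 9.3.
3. Add an embargo flag to the eCRF and code embargoed post-infusion items as not observable, never as no.
4. State whether vital status is embargoed. If it is, censor those patients in overall survival at CAR-T infusion and not at data capture.

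The cost is a few sentences, one eCRF field with a matching response code, and smaller stated denominators, hence wider intervals, for post-infusion items. No patient needs to be dropped and no reweighting is needed.
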